12.5 Data protection and patient confidentiality

The Chief Investigator will be the data custodian.

All information collected in the study will be kept strictly confidential.

The Chief Investigator and research team staff will comply with the requirements of the Data Protection Act and General Data Protection Regulation (and other applicable

regulations) concerning the collection, storage, processing and disclosure of personal information and will uphold the Act's core principles.

All digital data will be stored on a cloud-based drive (Loughborough University's OneDrive) on a University of Loughborough computer with the folder being password-protected. Data will only be shared with investigators involved with the study using Microsoft 365 groups, which provides secure, access-controlled, sharing options. Personal data will only be kept until the study closure upon which it will be destroyed. All paper records (informed consent and demographic & health questionnaire) will be stored in a locked filing cabinet in the responsible investigator's office (also locked). Data from the questionnaire will be pseudonymised and converted to a digital format before study closure. The hard copies of study documents will be destroyed upon study closure.

Analysis of the data generated will be undertaken by the Loughborough University Principal Investigator (or Loughborough University researchers) on Loughborough University premises.

Research data will be pseudonymised at Loughborough University before being transferred to the University of Leicester. Pseudonymised research data will be stored for 6 years after the study has ended.

Consent forms, enrolment logs and details of record linkage* (i.e., participant ID numbers/pseudonyms) will be kept for a minimum of 6 years after the study has ended as part of the research data so that in the event of the data being challenged, this will allow for verification of the quality of the data. At the end of this period, approval from the Sponsor will be requested for the destruction of the data.

Participant personal data, collected for the purposes of arranging the study visits, will only be accessed by the research team listed on this protocol. Participants will have signed a consent form to state they have read the participant information sheet and understood it involves data sharing among the research team only. Personal data will be deleted once they have been used for their agreed purpose. Where individuals have consented to receive a copy of the research findings, contact details will be retained until this time. Contact details will be stored securely and separately from participant's research data and clinical information.

The Trial Master File (TMF) will be kept in a folder in a locked cabinet/drawer in a secured room in a secure office environment office at the University of Leicester by the Chief Investigator (or delegate). An Investigator Site File (ISF) will be maintained by Loughborough University by the Principal Investigator (or delegate) in a folder in a locked cabinet/drawer in a secured room in a secure office environment.

Long-term storing will comply with the University of Leicester archiving Standard Operating Procedures.

12.6 Access to the final study dataset

The CI and their appointed deputies will have access to the analysed study dataset following execution of the SAP and completion of the End of Trial Report.

13 Finance and Insurance

13.1 Funding

This study is funded by a grant from the NIHR EME programme (funder ref NIHR158852). The funder will be responsible for funding the study but will not be part of the study conduct, data analysis and interpretation, manuscript writing, and dissemination of results.

13.2 Indemnity

Sponsorship and insurance for study design and management will be provided by the University of Leicester.

If a participant is harmed due to negligence and/or the conduct of the study, any claim will be covered by the Loughborough University indemnity arrangements against the risk of claims relating to research studies their staff design and undertake. If a study participant wishes to make a complaint about any aspects of the way they have been treated or approached during the research project, they may contact Loughborough University Research Governance Officer (details provided in Participant Information Sheet). They may also refer to Loughborough University's policies relating to Research Misconduct and Whistle Blowing which are available https://www.lboro.ac.uk/internal/research-ethics-integrity/research-integrity/.

14 Dissemination

14.1 Dissemination Policy

The research team owns the data arising from the study. On completion of the study, data will be analysed and tabulated. Upon completion, the data will be analysed and disseminated at relevant national and international conferences, and in journal articles.

EQ-5D-5L EuroQol EQ-5D-5L — Quality of Life questionnaire
EWGSOP2 European Working Group on Sarcopenia in Older People

FEV1 Forced expiratory volume in 1 second

GCP Good Clinical Practice

GP PAQ General Practice Physical Activity Questionnaire

HbA1c Haemoglobin A1C HD Haemodialysis

ICF Informed Consent Form
ISF Investigator Site File
ITT Intention-to-treat analysis
ISWT Incremental Shuttle Walk Test
KDQoL Kidney disease quality of life
LCTU Leicester Clinical Trials Unit

MCID Minimal clinically important difference
MedDRA Medical Dictionary for Regulatory Activities
NIHR National Institute for Health and Care Research

NMES Neuromuscular electrical stimulation

PI Principal Investigator

PIS Participant Information Sheet

PPIE Patient Participation, Involvement and Experience

PBMC Peripheral blood mononuclear cells

QoL Quality of Life

RCT Randomised Control Trial
RDN Research Delivery Network
REC Research Ethics Committee

RNA Ribonucleic acid

RPE Rating of perceived exertion
SAE Serious Adverse Event
SAP Statistical Analysis Plan
SAR Serious Adverse Reaction

SARC-F Strength, Ambulation, Rising from a chair, Stair climbing and history of Falling

SarQoL Sarcopenia related quality of life

SONG-HD Standardised Outcomes in Nephrology - Haemodialysis

SOP Standard Operating Procedure
SPPB Short Physical Performance Battery

STS5 Sit to Stand 5 STS60 Sit to Stand 60

SUSAR Suspected Unexpected Serious Adverse Reaction

TMF Trial Master File
TMG Trial Management Group

TSC Trial Steering Committee

UK Clinical Research Collaboration

UKRR UK Renal Registry

VO_{2Peak} Maximal Exercise Capacity

WBC White blood cells

KEY WORDS

Sponsor ref: 0968

Skeletal muscle wasting, physical function, chronic disease, quality of life.

STUDY SUMMARY

STUDT SUMMART								
Study Title		The use of neuromuscular electrical STIMulation as a treatment for sarcopenia in people on HaemoDialysis – STIM-HD						
Study Design	Prospective, open-label, asses Randomised Controlled Trial							
Study Participants	(home or unit-based), with sarcope on patient screening.							
Planned Sample Size Follow-up Duration	Sub-group for optional mechanistic 50 participants (25 in each assessments (high-den electromyography);	228 (114 to the intervention arm and 114 to the control arm) Sub-group for optional mechanistic outcomes: • 50 participants (25 in each arm) will take part in neuromuscular assessments (high-density surface and intramuscular electromyography); • 24 participants (12 per arm) will take part in skeletal muscle						
Planned Study Period	3.5 years							
	Objectives	End Points/Outcome Measures						
Primary	To measure the effect of a 3-month NMES programme on muscle strength, the core manifestation of sarcopenia, compared with standard care for HD patients	- Isometric strength						
Secondary	To measure the effect of a NMES programme on QoL.	Kidney Disease Quality of Life (KDQoL) questionnaire						
	To evaluate the cost-effectiveness of a NMES programme compared with standard care for patients with end-stage kidney disease within an NHS costing perspective	EuroQol EQ-5D-5LResource use questionnaire						
	To investigate if NMES results in neuromuscular adaptations and changes in muscle phenotype	 Skeletal muscle biopsy analysis High density and Intramuscular Electromyography Evoked responses to femoral nerve stimulation 						
	To investigate the effect upon muscle mass, physical function and physical activity levels	 Ultrasound 6-minute walk test or ISWT as space allows Short Physical Performance Battery Sit to stand 60 Bioelectrical impedance SARC-F questionnaire SarQoL questionnaire GP PAQ questionnaire Accelerometry Sleep diary Handgrip Strength 						
	To measure the safety of the intervention	Adverse Events relating to the intervention						

FUNDING AND SUPPORT IN KIND

FUNDER(S)	FINANCIAL AND NON-FINANCIAL SUPPORT
(Names and contact details of ALL organisations	GIVEN
providing funding and/or support in kind for this study)	
NIHR EME Programme	Financial support
Funder reference: NIHR158852	

ROLE OF STUDY SPONSOR

The Sponsor of this research is the University of Leicester. The University of Leicester is responsible for the design, management and outputs of the research. Participating NHS sites are responsible for the conduct of the study within their organisation.

The Research Governance Office review and approve all iterations of the protocol as part of their initial Sponsor review and amendment review process. Further information is available from our Sponsor Standard Operating Procedures webpage.

ROLE OF COLLBORATOR(S)

[name] and [name] will support recruitment at University Hospital Coventry and Warwickshire and University Hospitals Birmingham respectively.

[name] and [name] will lead the mechanistic neuromuscular adaptation investigation assessments.

[name] will oversee the heath economic analysis.

[name] will lead the PPIE work throughout the study.

ROLES AND RESPONSIBILITIES OF TRIAL MANAGEMENT COMMITTEES/GROUPS & INDIVIDUALS

The Leicester Clinical Trials Unit (LCTU) is providing support for this study. It is a UKCRC registered Clinical Trials Unit with extensive experience of handling data from large multi-centre trials. The LCTU has been involved in the development and design of the protocol since conception of this study and will facilitate study data collection, statistical analysis and reporting and associated quality assurance. The study is sponsored by the University of Leicester.

A Trial Management Group (TMG) including the CI, Trial Co-ordinator, co-applicants and members of the LCTU will direct and oversee the day-to-day running of the study and will meet according to its demands. The TMG will highlight any key day-to-day study-related issues and monitor progress of all research activities to ensure that the study is being delivered on time and to target.

An independent Trial Steering Committee (TSC), with an independent Chair, Expert Statistician, Health Economist, Clinician with relevant expertise, and Lay Representative will be convened to oversee, advise on and monitor the study. A Sponsor representative and a Research Network representative will also be invited to attend as non-voting observers. The TSC will meet at least annually or as required throughout the study. Meeting minutes will be sent to all members, the Sponsor, and the funder, and retained in the Trial Master File (TMF).

An independent Data Safety Monitoring Committee (DSMC), with an independent Chair, Expert Statistician, Clinician with relevant expertise, and Lay Representative will be convened to monitor the study data and make recommendations to the TSC on whether there are any ethical or safety concerns. The DSMC will meet at least annually or as required throughout the study. Meeting minutes will be sent to all members, the Sponsor, the funder, and the TSC, and retained in the TMF.

STUDY FLOW CHART

[figure not shown]

Figure 1: Flow of participants through the study

1. BACKGROUND

Sarcopenia is characterised by a loss of muscle strength (the most important characteristic), and mass, as well as low physical performance, and is now classified as a disease in its own right (1). Although often associated with ageing, it is also recognised as a complication of other long term health conditions and is associated with worse clinical outcomes, including poor quality of life (QoL), higher hospitalisation rates and increased mortality. The annual cost of sarcopenia to the NHS is around £2.5 billion (2).

Chronic kidney disease (CKD) is a public health emergency that threatens to overwhelm the NHS, affecting around 14% of adults in England (3). When kidney function drops to the point it can no longer sustain life, a form of renal replacement therapy is required, for example dialysis. There are currently 30,000 adults and children receiving dialysis in the UK, with this number projected to increase to 143,000 by 2033 (4). Sarcopenia is a frequent complication of CKD, affecting around 28% of people with more advanced disease (5-7). Data from our cohort of patients with kidney failure on haemodialysis (HD) shows it is common; 39% of patients have confirmed sarcopenia, a further 10% have probable sarcopenia, and 16% have severe sarcopenia (unpublished observations). Systematic reviews specifically in CKD patients have shown sarcopenia is associated with falls, fractures, cardiovascular events and mortality (7, 8), demonstrating its clinical importance. In the UK, sarcopenia is diagnosed according to the algorithm described and recently updated by the European Working Group on Sarcopenia in Older People (9) (EWGSOP2). Depending upon performance in a range of tests, people can be diagnosed with either probable sarcopenia (the point at which guidelines suggest an intervention should be targeted), confirmed sarcopenia, or severe sarcopenia.

2. RATIONALE

The mainstay of treatment for sarcopenia is lifestyle modification, principally exercise interventions. Exercise has been shown to improve muscle mass and strength in people with sarcopenia on haemodialysis (10, 11). Recent national guidelines from the UK Kidney Association, endorsed by the National Institute for Health and Care Excellence (NICE) and led by authors from this group, routinely recommend dialysis unit-based exercise programmes. Unfortunately, although exercise programmes are likely to be more beneficial from both a cardiovascular and a musculoskeletal point of view, as many as 74% of HD patients are unable or unwilling to participate in such programmes (12, 13). In the recently published CYCLE-HD and PEDAL trials (both undertaken by this group), which investigated dialysis unit-based exercise interventions, of the 2835 patients screened, over 2100 were deemed ineligible (12, 13). Many of the patients were severely deconditioned and adherence to the exercise interventions was extremely low (47% of exercise training sessions prescribed were completed and only 18% adhered exactly to the prescription) (14). Therefore, an accessible alternative is clearly needed.

Neuromuscular electrical stimulation (NMES) is a treatment whereby the application of intermittent electrical stimuli generates involuntary muscle contractions, and might serve as an 'exercise mimetic'. This therapy is used widely in physiotherapy rehabilitation programmes (15, 16) and is now being used in clinical settings, including in intensive care units (17). NMES could represent an ideal alternative for people on HD who are unable to exercise and therefore prevent the inevitable decline in muscle mass and strength that leads to sarcopenia.

3. RESEARCH QUESTION /OBJECTIVES AND OUTCOME MEASURES/ENDPOINTS

Research Question: Can NMES be used as a therapy for sarcopenia in people on HD?

Aim: To test the clinical efficacy of NMES as a therapy for sarcopenia in people on HD.

Objectives:

- To measure the effect of a 3-month NMES programme on muscle strength, the core manifestation of sarcopenia, compared with standard care for HD patients
- To measure the effect of a NMES programme on QoL
- To measure the effect of a NMES programme on muscle size and measures of physical function
- To evaluate the cost-effectiveness of a NMES programme compared with standard care for patients with end-stage kidney disease within an NHS costing perspective
- To investigate if NMES results in neuromuscular adaptations and changes in muscle phenotype

3.1 Primary objective

Primary Objective: To measure the effect of a 3-month NMES programme on muscle strength, the core manifestation of sarcopenia, compared with standard care for HD patients.

Null hypothesis: There will be no difference in the change in muscle strength from baseline to 3 months between NMES and standard care groups.

Experimental hypothesis: Three months of NMES will create a significant increase in muscle strength compared to the standard care group.

3.2 Secondary objectives

The secondary objectives are:

- To measure the effect of a NMES programme on QoL
- To evaluate the cost-effectiveness of a NMES programme compared with standard care for patients with end-stage kidney disease within an NHS costing perspective
- To investigate if NMES results in neuromuscular adaptations and changes in muscle phenotype
- To measure the effect of a NMES programme on muscle size and measures of physical function
- To measure the safety of the intervention

3.3 Outcome measures/endpoints

3.3.1 Primary endpoint/outcome

Primary Endpoint: The primary outcome is change in muscle strength measured using isometric dynamometry from baseline to 3-months.

3.3.2 Secondary endpoints/outcomes

Secondary endpoints:

To compare between randomised groups;

- 1. Additional efficacy measures
 - a. Muscle size and architecture (measured cross-sectional area of rectus femoris using ultrasound, muscle thickness and angle of fibre pennation)
 - b. Lower-extremity strength, functional capacity, and balance: The short physical performance battery (SPPB)
 - c. Cardiovascular functional capacity and endurance: the 6-minute walk test (or incremental shuttle walk test in the event of space constraints)
 - d. Body composition (including lean muscle mass) using bioelectrical impedance
 - e. Sit-to-stand-60 test (muscle endurance)
 - f. GP Physical Activity questionnaire
 - g. Hand Grip strength
 - h. Accelerometry and sleep diary
 - i. Isometric rate of force development
- 2. Measures of QoL and social functioning
 - a. The Kidney Disease Quality of Life tool (KDQoL)
 - b. EQ-5D-5L, a generic multi-attribute health related QOL questionnaire for use in cost utility analysis (health economic analysis).
 - c. Levels of fatigue (using SONG-HD score)
 - d. SARC-F (validated questionnaire recommended as the screening instrument for sarcopenia in clinical practice by the European Working Group)
 - e. Sarcopenia and quality of life (SarQoL questionnaire)
- 3. NHS Resource use (collected via participant self-completion questionnaire), to be combined with NHS unit costs for use in cost utility analysis
- 4. Measures of process and tolerability
 - a. Number of patients eligible, approached and recruited
 - b. Dropout rates and movement between allocated study groups
 - c. Tolerability of the intervention to include number of neuromuscular stimulation sessions undertaken and the total time per session (up to 30-minutes).
- 5. Measures of safety
 - a. Adverse events relating to the intervention
- Measures of neuromuscular adaptations and muscle phenotype
 - High-density surfacer electromyography, for assessment of quadriceps motor unit recruitment and discharge rate, and conduction velocity during sub-maximum and maximum knee extension contractions.

- b. Intramuscular electromyography, for assessment of motor unit potential jiggle and segment jitter, electrophysiological markers of neuromuscular junction transmission stability.
- c. Femoral nerve stimulation, for assessment of quadriceps contractile properties.
- d. Skeletal muscle biopsy analysis

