3.4 Table of endpoints/outcomes

Objectives	Outcome Measures	Timepoint(s) of evaluation of this outcome measure (if applicable)
Primary Objective: To measure the effect of a 3-month NMES programme on muscle strength, the core manifestation of sarcopenia, compared with standard care for HD patients	Isometric strength	Screening visit (as a familiarisation session), baseline, 3, 6, 9 months post randomisation
Secondary Objectives To measure the effect of a NMES programme on QoL	The Kidney Disease Quality of Life tool (KDQoL)	Baseline, 3, 6, 9 months post randomisation
To evaluate the cost-effectiveness of a NMES programme compared with standard care for patients with end-stage kidney disease within an NHS costing perspective – health economic evaluation	EQ-5D-5L questionnaire Resource use questionnaire	Baseline, 3, 6, 9 months post randomisation
To measure the effect of a NMES programme on muscle size and measures of physical function	Muscle mass (thickness and cross- sectional area by ultrasound) Muscle quality and architecture (e.g. echo intensity and angle of pennation by ultrasound)	Baseline, 3, 6, 9 months post randomisation
	Handgrip strength by dynamometry	
	Lower-extremity strength, functional capacity, and balance (using the short physical performance battery (SPPB)) and Sit to stand 60.	
	Cardiovascular functional capacity and endurance (by the 6-minute walk test or the ISWT if space constraints)	
	Body composition (using bioelectrical impedance)	
	Muscle endurance (using the Sit-to- stand-60 test muscle endurance)	
	Isometric rate of force development	
	Physical activity levels (using GP Physical Activity questionnaire and accelerometry)	

To investigate if NMES results in neuromuscular adaptations and changes in muscle phenotype	Levels of fatigue (using SONG-HD score) Perception of muscle function (using the SarQoL questionnaire) Indices of sarcopenia (using the SARC-F questionnaire). Motor unit recruitment, and discharge rate, and conduction velocity (using high density electromyography) Motor unit potential jiggle and segment jitter (using intramuscular electromyography) Evoked quadriceps contractile properties Skeletal muscle biopsy analysis	Baseline, 3-months post randomisation.
To measure the safety of the intervention	Adverse Events relating to the intervention	3-months post randomisation

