The participant starts from a seated position on a hard, upright chair (such as a dining chair), with the feet flat on the floor and the knees bent at 90°. For the test, the participant simply stands up fully and then sits down again to the starting position, without using the hands (one cycle). The length of time in seconds that it takes for the individual to complete 5 repetitions is recorded.

6) Sit to Stand 60 test

The participant starts from a seated position on a hard, upright chair (such as a dining chair), with the feet flat on the floor and the knees bent at 90°. For the test, the participant simply stands up fully and then sits down again to the starting position, without using the hands (one cycle). The number of cycles achieved in 60 seconds will be recorded to provide a surrogate measure of muscular endurance.

7) Six-minute walk test

Cones are placed up to 10-30m apart (depending upon space available) and the individual is asked to walk as far as they can in 6 minutes. Distance walked in meters is recorded.

8) Incremental shuttle walk test (ISWT)

The participant walks a level 10m shuttle course at a speed controlled by an external audible bleep signal. The bleep speed progressively increases at 1 minute intervals for a total of 12 stages, and the test is terminated when the participant fails to complete the shuttle course in the allowed time, or reaches volitional exhaustion. We may also ask participants to wear the accelerometer during this test (see section below on accelerometry).

9) Bioelectric Impedance Analysis (BIA)

BIA analysis will be carried out using a free-standing BIA monitor. This is a painless, non-invasive method for measuring fat and fat free mass. Participants will stand on the monitor platform in bare feet and grip the handles firmly while the monitor takes the measurement. The procedure takes around two minutes.

10) Accelerometry

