11.3.4 Analyses of secondary outcomes

The secondary outcomes will be analysed in a similar manner to the primary outcome. All represent continuous data and therefore linear regression will be used. All analyses will be adjusted for baseline value and the stratification factors. The number of deaths and cardiovascular events expected is relatively low, therefore formal time to event analyses will not be conducted. Kaplan–Meier will be presented to describe the relationship between these events and treatment.

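### The section 11.3.4 regression rule cannot apply to several listed secondary endpoints, and the single walking endpoint mixes two tests with no explicit same-test rule and no test term

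*Protocol*

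**What the plan says.** Section numbers refer to the randomised-trial protocol, not to the pilot (WP1) protocol bound with it.

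- **Endpoints.** Section 3.3.2 sets out secondary endpoints for comparison between the randomised groups. Besides functional tests and questionnaires, it includes recruitment numbers, "Dropout rates and movement between allocated study groups", the number and length of NMES sessions, and adverse events linked to the intervention.
- **Analysis rule.** Section 11.3.4 says of the secondary outcomes: "All represent continuous data and therefore linear regression will be used". It adds: "All analyses will be adjusted for baseline value and the stratification factors".
- **Walking endpoint.** Section 3.3.2 gives "the 6-minute walk test (or incremental shuttle walk test in the event of space constraints". Section 3.4 repeats the choice: "Cardiovascular functional capacity and endurance (by the 6-minute walk test or the ISWT if space constraints".
- **The two tests (section 8.7).** For the 6-minute walk, "Cones are placed up to 10-30m apart (depending upon space available" and "Distance walked in meters is recorded". For the incremental shuttle walk test (ISWT), "The participant walks a level 10m shuttle course at a speed controlled by an external audible bleep signal"; no result or unit is given. The baseline data list in section 11.3.1 names the 6-minute walk distance only.

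**The concern.** There are two separate problems.

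First, section 11.3.4 is worded to cover every secondary outcome, but several items in section 3.3.2 are counts or proportions, lack a baseline value, arise before allocation, or exist in one arm only. An analyst who follows the sentence cannot carry it out for them, so a correct SAP would have to contradict the protocol.

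Second, one endpoint is filled by a self-paced timed walk or by an externally paced incremental test, depending on the space available, and the 6-minute course itself varies in length. The protocol does not explicitly keep test and course constant within a participant, and the stated covariates include neither. At stake are the meaning of an effect expressed in metres and the precision with which it is estimated.

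**Working it through.** **Part A: the rule set against the endpoint list**

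| Endpoint (3.3.2) | Type | Baseline value | Arms | Treated elsewhere |
|---|---|---|---|---|
| Recruitment numbers | count | none | arise before allocation | no |
| Dropout | proportion | none | both | 11.3.2: reasons for missing data reported |
| Crossover | count | none | both | 11.3.2: numbers, direction and reasons reported under CONSORT |
| NMES sessions, session time | count, minutes | none | NMES only | no |
| Intervention-related adverse events | count or proportion | none | control receives no NMES course | 10.3: SAEs tabulated by arm, no formal test |

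The session row follows from the schedules: NMES at each dialysis session appears in section 7.1 only, and section 7.2 shows NMES at screening alone. For adverse events, section 3.4 gives 3 months as the only time of evaluation. The schedules do mark an adverse event check at the baseline visit, but baseline measurements precede randomisation (8.6), so apart from a possible single try-out session (8.4) there is no intervention for an event to be related to. Deaths and cardiovascular events receive only descriptive Kaplan-Meier curves, in section 11.3.4 itself.

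The factors that section 11.3.4 calls stratification factors are called minimisation factors (age, time on dialysis) in sections 8.6, 11.3.3 and 11.5.

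**Part B: the walking endpoint**

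*The plan's own figure.* Section 11.1 gives a difference of 21.7 Nm, SD 47.5 Nm, 90% power, 5% significance (two-sided assumed) and 10% attrition.

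- n per arm = 2(1.960 + 1.282)² × (47.5/21.7)² = 2 × 10.51 × 4.79 = 100.7, so 101. Then 101/0.9 = 112.2, so 113 per arm and 226 in total.
- With the t distribution, n = 102. Then 102/0.9 = 113.3, so 114 per arm and 228 in total, as stated.

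The protocol gives no effect size or power for the walking endpoint, so all walking values below are assumptions.

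*Pooled effect.* With share w on the ISWT and effects dA (6-minute walk) and dB (ISWT), one regression estimates about (1 − w)dA + w·dB. Take dA = 30 m and dB = 18 m:

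- w = 0: 30 m
- w = 0.2: 0.8 × 30 + 0.2 × 18 = 27.6 m
- w = 0.4: 0.6 × 30 + 0.4 × 18 = 25.2 m

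Range: at w = 0.4, dB of 15, 30 or 45 m gives 24, 30 or 36 m.

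*Simulation.* Means 320 m (SD 100) and 200 m (SD 90); within-test correlation 0.9² = 0.81; 102 per arm; change regressed on arm and baseline; 3,000 runs per scenario.

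| ISWT share | Switch test between visits | Mean estimate (m) | SE | Power | Type I error | Power with test terms |
|---|---|---|---|---|---|---|
| 0% | 0% | 29.9 | 8.22 | 0.953 | 0.053 | not needed |
| 20% | 0% | 27.7 | 8.21 | 0.922 | 0.055 | 0.916 |
| 20% | 10% | 27.3 | 9.63 | 0.815 | 0.052 | 0.904 |
| 40% | 0% | 25.2 | 8.10 | 0.878 | 0.049 | 0.891 |
| 40% | 10% | 24.9 | 9.54 | 0.752 | 0.048 | 0.875 |

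Switching costs 0.922 − 0.815 = 0.107 or 0.878 − 0.752 = 0.126 of power. The standard error rises by 9.63/8.21 − 1 = 17% or 9.54/8.10 − 1 = 18%. One isolated switch matters little: (320 − 200)/102 = 1.2 m on an arm mean. The effect of course length is not quantified, because the protocol gives no figure for it.

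*Counts.* Comparing two means of overdispersed counts (means 0.1 to 20, 102 per arm) gave type I error of 0.046 to 0.055.

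**The case against.** **Details belong to the SAP.** Section 11.3 leaves full analysis detail to a SAP that is not shown. This stands for how two walk tests are modelled or combined. It does not rescue section 11.3.4, which states a rule rather than leaving one open. Nor can a later SAP recover which test and course were used if that was not recorded at the visit.

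**Switching should be rare.** Section 8.10 says the baseline assessments are repeated, the choice of test is driven by space, and section 6.2 excludes people planning to change centre within 6 months. This largely stands: within-participant switching is probably the exception, and the 10% above is only an assumption. Even so, follow-up runs to 9 months, assessments may be split over visits (8.7), and no sentence requires the same test or course.

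**Safety and crossover are handled elsewhere.** Sections 10.3, 11.3.2 and 11.3.4 give SAEs, crossover, deaths and cardiovascular events a descriptive treatment. This is true and limits the harm, but it also shows that the all-inclusive sentence contradicts the rest of the protocol.

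**Stronger readings that a reader might infer.**
- That metres from both tests will be pooled and the result will be uninterpretable. The protocol never says they are pooled and gives no ISWT unit; pooling is only inferred from one endpoint plus one rule. Even if pooled, type I error stayed at 0.048 to 0.055.
- That linear regression is an invalid model for counts. The check above does not support this, and regressing a 0/1 outcome on arm estimates a risk difference. What fails is the baseline term and the comparison of quantities that do not exist in both arms.

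**Conclusion.** The section 11.3.4 rule is wrong as written. It cannot be applied to recruitment numbers, dropout, crossover, NMES sessions or intervention-related adverse events, and it disagrees with the protocol's own descriptive handling of several events. This rests on the text alone.

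The walking endpoint calls for a cheap improvement. Under the assumed values, the effect in metres moves from 30 to about 25 m as ISWT use rises to 40% (24 to 36 m over the range of assumed ISWT effects). If 10% switch test between visits, power falls by about 11 to 13 percentage points; test terms in the model recover most of this. These sizes are illustrative, since the protocol documents neither the share of each test nor any switching.

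Only secondary endpoints are affected. The primary analysis and N = 228 are unchanged.

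**What to change.** In section 11.3.4:

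- Limit linear regression with baseline adjustment to continuous outcomes that have a baseline value.
- Report adverse events, dropout and crossover by arm as counts or proportions, with risk or rate differences and no baseline term. Keep the existing descriptive treatment of SAEs, deaths and cardiovascular events.
- Describe recruitment numbers overall, and session number and time in the NMES arm only.
- Replace stratification with minimisation factors.

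For the walking endpoint (sections 3.3.2, 3.4, 8.7 and 8.10):

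- Require the same walk test and course length for each participant at all visits, and record both.
- State what the ISWT result is and its unit.
- Analyse the 6-minute walk and the ISWT separately, or combine them only as within-test standardised effects.

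The cost is protocol and SAP wording plus a CRF entry for test and course. The downside is that each walking test is analysed on fewer participants.
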